4.2. Overall Study Duration

The study begins when the first participant signs the ICF. The end of the study is expected to occur when the last participant reaches their 6-month follow-up visit.

Completers (of treatment) are defined as participants who complete 30 days of study treatment administration (Day –3 to Day 26). A participant is considered to have completed the study if he/she has completed all periods of the study including the 6-month follow-up for which a disease assessment is required.

4.3. Study Termination

The investigator retains the right to terminate study participation at any time, according to the terms specified in the study contract. The investigator is to notify the IRB in writing of the study's completion or early termination, send a copy of the notification to the sponsor or sponsor's designee, and retain 1 copy for the site study regulatory file.

The sponsor may terminate the study electively, if required by regulatory decision or upon advice of the internal DSMB. If the study is terminated prematurely, the sponsor will notify the investigators, the IRBs, and regulatory bodies of the decision and reason for termination of the study. The DSMB will recommend termination of the study if warranted, as described in Section 11.7.

5. STUDY POPULATION

Deviations from eligibility criteria are not allowed because they can potentially jeopardize the scientific integrity of the study, regulatory acceptability, and/or participant safety. Therefore, adherence to the criteria as specified in the Protocol is essential. Prospective approval of Protocol deviations to recruitment and enrollment criteria, also known as Protocol waivers or exemptions, are not permitted.

5.1. Inclusion Criteria

Participants are eligible to be included in the study only if all of the following criteria apply:

1. Part 1: Male or female, 12 years of age or older. The participant (or legally acceptable representative for participants < 18 years of age) has the ability to comprehend and provides written informed consent for the study.

Note: The participants who are < 18 years of age will have a parent or legal guardian able to give written informed consent and assent (as appropriate) according to institutional standards and to comply with all study visits and procedures.

Part 2: Male or female, 18 years of age or older.

2. Eligible to receive an IEC therapy that is approved by the health authority in the country where the study is being conducted, for hematologic indications.

Part 1: Eligible to receive any IEC therapy for any approved indication.

Part 2: Eligible to receive Yescarta for relapsed or refractory large B-cell lymphoma or follicular lymphoma.

3. ECOG performance status 0 to 1.

4. Willingness to avoid pregnancy or fathering children based on the criteria below.

- a. Men must agree to take appropriate precautions to avoid fathering children (with at least 99% certainty) from screening through safety follow-up and must refrain from donating sperm during this period. Permitted methods that are at least 99% effective in preventing pregnancy (see [Appendix A](#)) should be communicated to the participants and their understanding confirmed.
- b. Women of childbearing potential must have a negative serum pregnancy test at screening and before the first dose on Day 1 and must agree to take appropriate precautions to avoid pregnancy (with at least 99% certainty) from screening through safety follow-up. Permitted methods that are at least 99% effective in preventing pregnancy (see [Appendix A](#)) should be communicated to the participants and their understanding confirmed.
- c. Women of nonchildbearing potential (ie, surgically sterile with a hysterectomy and/or bilateral oophorectomy OR ≥ 12 months of amenorrhea) are eligible.

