8.3.5.1. Pregnancy Testing

A serum pregnancy test will be required for all women of childbearing potential during screening, the Day 28 visit, and the 30-day follow-up visit. A urine or serum pregnancy test may be collected on Day -3 before administration of itacitinib. If the participant is going to hospice, the Day 28 pregnancy test may be omitted. Additionally, urine pregnancy tests should be performed as medically indicated (eg, in case of loss of menstrual cycle, when pregnancy is suspected). If a urine pregnancy test is positive, the results should be confirmed with a serum pregnancy test.

If the serum pregnancy test is negative after a urine test was positive, the investigator will assess the potential benefit/risk to the participant and determine whether it is in the participant's best interest to resume itacitinib and continue participation in the study.

If a pregnancy is confirmed by a serum pregnancy test, see Section 9.7 for reporting requirements.

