APPENDIX A. INFORMATION REGARDING EFFECTIVENESS OF CONTRACEPTIVE METHODS

For male participants in the study:

Male participants should use a condom from screening through 90 days after the end of systemic exposure. If the male participant has a partner that is of child-bearing potential, the partner should also use contraception through 90 days after the end of relevant systemic exposure. In addition, male participants must refrain from donating sperm from screening through 90 days after the end of relevant systemic exposure. Males who have had a vasectomy qualify as having met the requirement for a highly effective birth control method.

For female participants in the study:

The following methods that can achieve a failure rate of less than 1% per year when used consistently and correctly are considered as highly effective birth control methods:

- Combined (estrogen and progestogen containing) hormonal contraception associated with inhibition of ovulation^a
 - oral
 - intravaginal
 - transdermal
- Progestogen-only hormonal contraception associated with inhibition of ovulation^a
 - oral
 - injectable
 - implantable^b
- Intrauterine device^b
- Intrauterine hormone-releasing system^b
- Bilateral tubal occlusion^b
- Vasectomized partner^{bc}
- Sexual abstinence^d

Acceptable birth control methods that result in a failure rate of more than 1% per year include:

- Progestogen-only oral hormonal contraception, where inhibition of ovulation is not the primary mode of action
- Male or female condom with or without spermicide^e
- Cap, diaphragm, or sponge with spermicide^e
- Tubal ligation

^a Hormonal contraception may be susceptible to interaction with the investigational medicinal product, which may reduce the efficacy of the contraception method.

^b Contraception methods that in the context of this guidance are considered to have low user dependency.

^c Vasectomized partner is a highly effective method of avoiding pregnancy provided that partner is the sole sexual partner of the woman of childbearing potential study participant and that the vasectomized partner has received medical assessment of the surgical success.

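### Inclusion criterion 4c treats 12 months without periods, whatever the cause, as nonchildbearing potential, and so lifts the protocol's mandatory pregnancy tests and contraception agreement

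*Protocol*

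**What the plan says.** Criterion 4 in Protocol Section 5.1 sets the pregnancy-avoidance rules in three parts: 4a for men, 4b for women of childbearing potential, and 4c for women of nonchildbearing potential.

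- **4b, testing:** "Women of childbearing potential must have a negative serum pregnancy test at screening and before the first dose on Day 1".
- **4b, contraception:** the same women "must agree to take appropriate precautions to avoid pregnancy (with at least 99% certainty) from screening through safety follow-up".
- **4c:** women of nonchildbearing potential are eligible without those duties. The definition, introduced by ie, is "surgically sterile with a hysterectomy and/or bilateral oophorectomy OR ≥ 12 months of amenorrhea".
- **Section 8.3.5.1, scheduled tests:** "A serum pregnancy test will be required for all women of childbearing potential during screening, the Day 28 visit, and the 30-day follow-up visit". The same section also allows a Day -3 sample before dosing, by urine or serum.
- **Section 8.3.5.1, unscheduled tests:** "urine pregnancy tests should be performed as medically indicated (eg, in case of loss of menstrual cycle, when pregnancy is suspected". This sentence is not limited by childbearing status.
- **Appendix A**, in its list for female participants, names hormonal methods that act by suppressing ovulation, among them "Progestogen-only hormonal contraception associated with inhibition of ovulation". A footnote cautions that such methods may interact with the investigational product and lose efficacy.
- **Section 9.7** requires study treatment to stop at once when a pregnancy is confirmed. Section 7.1.1 lists pregnancy among the mandatory reasons for withdrawal from treatment.

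**The concern.** The surgical limb of 4c names the procedures that count. The amenorrhea limb names only a duration. It does not ask why periods are absent, how old the participant is, or whether she is menopausal.

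That matters in this population. Part 2 enrols relapsed or refractory lymphoma, and exclusion criterion 7 presupposes earlier anticancer therapy. Appendix A anticipates that some participants will use hormonal methods. Amenorrhea with a cause other than menopause is therefore foreseeable. That such amenorrhea need not mean inability to conceive is general medical knowledge. The documents do not say it, and it is treated here as an assumption.

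At stake is a participant-safety rule. The protocol clearly wants to prevent exposure in pregnancy, since it sets contraception duties for both sexes and orders treatment stopped on a positive finding. A definition that is too wide at entry lets the preventive steps be passed over and leaves only the reaction afterwards.

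**Working it through.** No calculation applies, because the point concerns an eligibility definition. The check reads the relevant texts against each other.

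1. **Is 4c a definition or an illustration?** It is introduced by ie, so it defines the class. A woman who meets either limb is in it.
2. **Does any text narrow the amenorrhea limb?** The texts checked were Table 3 of the Protocol, Sections 5.1, 7.1.1, 8.3.5.1 and 9.7, Appendix A, the amendment summary in Appendix G, and the SAP. None ties amenorrhea to menopause, age, cause or laboratory confirmation. Appendix A does not define childbearing potential at all.
3. **Can a site read in a narrower meaning?** The opening of Section 5 forbids deviations from the eligibility criteria and asks for adherence to them as specified. A site that applies 4c literally is following the protocol.
4. **What does a woman classed under 4c fall outside?**
   - the serum test at screening (4b, Section 8.3.5.1);
   - the test before the first dose (4b requires it; Section 8.3.5.1 words the Day -3 sample as optional);
   - the serum test at Day 28;
   - the serum test at the 30-day follow-up;
   - the contraception agreement from screening through safety follow-up (4b).

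   That makes four scheduled testing occasions (3 serum tests in Section 8.3.5.1 + 1 pre-dose test) and one contraception duty.
5. **What remains for her?** The medically indicated urine tests of Section 8.3.5.1. These need a clinical trigger, so they do not replace a test before dosing.
6. **How does this fit the rest of the protocol?**
   - Section 8.3.5.1 gives loss of the menstrual cycle as a reason to test, whereas 4c takes long absence of periods as sufficient to end scheduled testing.
   - Appendix A counts ovulation-inhibiting hormonal methods as contraception and warns that they may be weakened. Under 4c, a woman amenorrheic for a year on such a method leaves both the testing and the contraception rules.
   - Section 9.7 demands immediate discontinuation on a confirmed pregnancy, but for these women no scheduled test would look for one.

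**The case against.** The best defence is that the amenorrhea limb is familiar shorthand for postmenopause and that sites will read it so. Investigators may still test when they see reason to, and exclusion criterion 13 lets them exclude a participant at significant risk. IEC therapy follows its prescribing label, and conditioning follows standard of care; either may bring its own pregnancy testing. This has some force for actual practice. It does not repair the text, because 4c never mentions menopause, and what labels or local practice require cannot be seen from these documents.

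Several stronger readings are tempting, and the documents do not support them:

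- **That these women skip every pregnancy test.** The as-indicated urine tests still apply to them, and the pregnancy row in Table 3 carries no restriction by childbearing status.
- **That 4c contradicts Appendix A.** Appendix A lists methods by effectiveness and never mentions amenorrhea. Its interaction footnote is a caution only, and Section 2.2.1 reports that itacitinib neither inhibited nor induced CYP activity. This is a tension to reconcile.
- **That 4c contradicts Section 8.3.5.1.** New loss of periods on study differs from a year's absence established at entry, so this too is a tension.
- **That girls who have not yet menstruated are exempted.** Part 1 does admit them by age ("Part 1: Male or female, 12 years of age or older"), but 4c speaks of women and does not say whether never having menstruated counts as amenorrhea. The question cannot arise from age in Part 2, which starts at 18.
- **That a count of affected women can be given.** If 40% of the 108 planned participants (62 + 46) were women, that would be about 43. If 5% to 20% of those had such amenorrhea, the count would be about 2 to 9 (43 × 0.05 = 2.2; 43 × 0.20 = 8.6). Neither percentage is in the documents, and 26 Part 1 participants had already enrolled by 08 JAN 2021, beyond the reach of any change now.

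**Conclusion.** The point holds as a defect in a stated eligibility rule. On the text, 12 months of amenorrhea from any cause is enough to take a woman out of the mandatory pregnancy tests and the contraception agreement, and she can be dosed on that basis.

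Per woman, the size is four scheduled testing occasions and one contraception duty. The number of women cannot be derived, because the documents give no split by sex or age and no data on amenorrhea. The practical harm rests on the assumption stated above, that amenorrhea with a cause other than menopause can leave a woman able to conceive.

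A reader might infer that the trial's results are at risk. They are not: no endpoint, analysis set, sample size or test depends on criterion 4c. The case for acting is participant safety, set against a very small cost of correction.

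**What to change.** Reconcile criterion 4c with Section 8.3.5.1 and Appendix A. Qualify the amenorrhea limb so that amenorrhea with another explanation does not by itself remove a participant from the tests and contraception rules the protocol already contains. The sponsor's medical team should set the wording and decide which explanations it covers, including whether it extends to Part 1 participants who have not yet menstruated.

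The cost is one clause in criterion 4c, in a protocol amendment. The downside is a few more pregnancy tests, all at visits already scheduled. No analysis changes.

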5.2. Exclusion Criteria

Participants are excluded from the study if any of the following criteria apply:

1. Evidence of active uncontrolled/untreated infection (viral, bacterial, fungal, opportunistic) of any origin.
2. Evidence of active HBV or HCV infection as defined in Section [8.3.5.2](#).
3. Known human immunodeficiency virus.
4. Active acute or chronic GVHD requiring systemic therapy.
5. Concurrent use of chronic systemic steroids or immunosuppressant medications.
6. Known hypersensitivity or severe reaction to itacitinib, similar compounds, or excipients of itacitinib.
7. Any unresolved toxicity \geq Grade 2 (except stable Grade 2 peripheral neuropathy or alopecia) from previous anticancer therapy.
8. Participants with a known history or prior diagnosis of immunologic or inflammatory/autoimmune disease affecting the CNS, and unrelated to their disease under study or previous treatment.
9. Clinically significant or uncontrolled cardiac disease, including unstable angina, acute myocardial infarction within 6 months from Day –3 of itacitinib administration, New York Heart Association Class III or IV congestive heart failure, and circulatory collapse requiring vasopressor or inotropic support. Participants with arrhythmias that are not stable on a medical management program within 2 weeks of induction Day –3 are also excluded.
10. Central nervous system status:
 - a. Acute lymphoblastic leukemia participants with the following CNS status are eligible only in the absence of neurologic symptoms suggestive of CNS leukemia, such as cranial nerve palsy:
 - CNS1, defined as absence of blasts in CSF on cytospin preparation, regardless of the number of WBCs.
 - CNS2, defined as presence of $< 0.5 \times 10^9/L$ WBCs in CSF and cytospin positive for blasts, or $> 5/\mu L$ WBCs, but negative by Steinherz/Bleyer algorithm:
 - CNS2a: $< 1.0 \times 10^9/L$ RBCs; $< 0.5 \times 10^9/L$ WBCs and cytospin positive for blasts.
 - CNS2b: $\geq 1.0 \times 10^9/L$ RBCs; $< 0.5 \times 10^9/L$ WBCs and cytospin positive for blasts.
 - CNS2c: $\geq 1.0 \times 10^9/L$ RBCs; $\geq 0.5 \times 10^9/L$ WBCs and cytospin positive for blast, but negative by Steinherz/Bleyer algorithm.

b. Diffuse large B-cell lymphoma participants: Participants must have no signs or symptoms of CNS disease or detectable evidence of CNS disease; participants who have been previously treated for CNS disease but have no evidence of disease at screening are eligible.

11. Participants who are currently breastfeeding.

12. Receipt of a prior investigational study agent within 4 weeks before screening visit.

Note: Participants who have received anti-CD19 IEC therapy on a study where cell infusion occurred greater than 4 weeks before the screening visit are NOT excluded.

13. Any condition that would, in the investigator's judgment, interfere with full participation in the study, including administration of itacitinib and attending required study visits (if outpatient); pose a significant risk to the participant; or interfere with interpretation of study data.

14. Inability of the participant to swallow and retain oral medication.

15. Participants with laboratory values at screening defined in [Table 8](#).

Table 8: Exclusionary Laboratory Values

Laboratory Parameter		Exclusion Criterion
Hematology		
a	Platelets	$\leq 10 \times 10^9/L$
b	Hemoglobin	$\leq 8 \text{ g/dL}$
Hepatic		
e	ALT	$\geq 2.5 \times \text{ULN}$ for age, $> 5 \times \text{ULN}$ in the presence of liver metastases
f	AST	$\geq 2.5 \times \text{ULN}$ for age, $> 5 \times \text{ULN}$ in the presence of liver metastases
g	Total bilirubin	$> 1.5 \times \text{ULN}$ or $> 3 \times \text{ULN}$ in the presence of documented Gilbert's syndrome (unconjugated hyperbilirubinemia)
Renal		
h	Creatinine clearance	
Participants ≥ 18 years of age: $\leq 50 \text{ mL/minute}$ based on Cockcroft-Gault formula.
 
Participants < 18 years of age: GFR < 15 based on revised Schwartz formula 2009.
 
The cutoffs for mild, moderate, and severe renal insufficiency based on Cockcroft-Gault are 60-90 mL/min, 30-59 mL/min, and 0-29 mL/min, respectively.
 
Note: Creatinine clearance necessitates a 24-hour urine sample before the blood draw to calculate. An estimated value is acceptable.

Cardiopulmonary		
i	Cardiac LVEF	$\leq 40\%$ confirmed by ECHO/multigated analysis
j	Adequate pulmonary function	$\geq \text{Grade 2 dyspnea}$ and $\geq \text{Grade 2 hypoxia}$

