3. STUDY DESIGN

3.1. Overall Study Design

This is a 2-part Phase 2 study designed to assess the safety and efficacy of oral administration of itacitinib for the prevention of CRS in male or female participants planning to receive IEC therapy for any approved hematologic indication.

- In Part 1, approximately 62 participants older than 12 years will be administered itacitinib 200 mg QD (open label). Based on the Protocol-defined analysis in Protocol Amendment 2, 10 participants with ALL will be included.
- In Part 2, approximately 46 evaluable participants older than 18 years will be randomized to receive either itacitinib 200 mg BID or placebo.

This study includes a 14-day screening period after apheresis. Apheresis will be per institutional standard of care. Conditioning chemotherapy will be administered at the discretion of the investigator.

Participants will be administered study drug beginning at Day -3 to Day -1 before IEC infusion. Immune effector cell therapy will be administered on Day 0 along with study drug. Participants will continue to receive study drug through Day 26 to complete a 30-day study treatment period.

During the treatment period, Protocol-defined assessments will be conducted on Day -3, Day -1, Day 0 (IEC infusion day), Day 1, Day 3, Day 5, Day 7, Day 14, Day 21, and Day 28. Restaging of hematologic disease will be conducted per institutional guidelines. Completers are defined as participants who complete 30 days of itacitinib administration (Day -3 to Day 26). An EOT assessment will be conducted at Day 28 ± 2 days. Additional post-therapy follow-up visits will be conducted 30 days after the last dose of itacitinib and 90 and 180 days after IEC infusion. End of study is met at Day 180.

Safety will be monitored beginning at screening and will continue through to a 30-day post-treatment safety follow-up visit.

Hematologic disease assessments should be conducted as indicated in the SoA. The date of the assessment as well as the results should be recorded in the eCRF.

A planned interim analysis for CRS futility will be conducted when 24 participants in Part 1 are treated with an approved IEC therapy and complete the Day 28 (EOT) visit. The study may be stopped for futility at the interim analysis if the conditional power based on interim results is lower than 20%, which is equivalent to more than 17 out of 24 participants experiencing \geq Grade 2 CRS by Day 14.

See [Figure 1](#) and [Figure 2](#) for the study design.

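### Protocol 5.2 criterion 10a gives CSF white-cell cuts that differ 100-fold within the CNS2 definition (0.5 × 10^9/L, which is 500/µL, against 5/µL), so the intended entry rule for ALL participants with CSF blasts is unclear

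*Protocol*

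**What the plan says.** Protocol Section 5.2, criterion 10a, makes ALL participants eligible by CNS class, provided they have no neurologic symptoms pointing to CNS leukemia. Two classes are listed.

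- CNS1: "CNS1, defined as absence of blasts in CSF on cytospin preparation, regardless of the number of WBCs".
- CNS2, first limb: "WBCs in CSF and cytospin positive for blasts", with the count set below 0.5 × 10^9/L.
- CNS2, second limb, offered as an alternative to the first: "> 5/\mu L$ WBCs, but negative by Steinherz/Bleyer algorithm".

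Three subtypes follow.

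- CNS2a and CNS2b both take a positive cytospin with a white-cell count under 0.5 × 10^9/L. They differ only in red cells, which lie under 1.0 × 10^9/L for CNS2a and at or above that figure for CNS2b.
- CNS2c requires red cells at or above 1.0 × 10^9/L and white cells at or above 0.5 × 10^9/L, and is worded as "WBCs and cytospin positive for blast, but negative by Steinherz/Bleyer algorithm".

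The opening of Protocol Section 5 forbids deviations from eligibility criteria and rules out waivers. SAP Section 3.1, referring to Protocol Amendment 2, states for Part 1 that "10 participants with ALL will be included".

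**The concern.** An eligibility criterion should give the same answer at every site. Here one sentence states a white-cell cut in two units, and the two values do not agree. The algorithm check is attached to the lower figure in the CNS2 definition and to the higher figure in the subtype that carries it. Neither the Protocol nor the SAP gives another CSF cut that would show which was meant.

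What is at stake is the entry of ALL participants who have blasts in the CSF. The class is also used later: SAP Section 6.1.2 summarises CNS status at baseline for ALL, and Protocol Appendix F defines CNS remission and relapse in terms of CNS-1, CNS-2 and CNS-3 status.

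**Working it through.** **Unit conversion.** The inputs are the figures in criterion 10a, with 1 L = 10^6 µL.

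- First limb and CNS2a to CNS2c: 0.5 × 10^9 per L ÷ 10^6 = 500/µL.
- Second limb: 5/µL × 10^6 = 5 × 10^6 per L = 0.005 × 10^9/L.
- Ratio: 500 ÷ 5 = 100.
- Red cells: 1.0 × 10^9 per L ÷ 10^6 = 1000/µL, the same in all three subtypes. There is no conflict here.

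The 0.5 × 10^9/L figure appears four times for white cells (the definition and three subtypes). The 5/µL figure appears once. A fault in reading the PDF is therefore unlikely to explain the mismatch.

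**What the text does to individual participants.** All rows are cytospin positive. The fourth and fifth columns apply the criterion literally. The last replaces 0.5 × 10^9/L by 5/µL throughout. It is an illustration only, not a view on which value is right.

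| WBC/µL | RBC/µL | Algorithm | CNS2 limbs met, as written | Subtype as written | Result with 5/µL throughout |
|---|---|---|---|---|---|
| 3 | 5000 | either | first | CNS2b | CNS2b |
| 50 | 5000 | negative | both | CNS2b | CNS2c |
| 50 | 5000 | positive | first | CNS2b | no CNS2 class |
| 50 | 100 | negative | both | CNS2a | CNS2 by second limb, no subtype |
| 50 | 100 | positive | first | CNS2a | no CNS2 class |
| 600 | 5000 | negative | second | CNS2c | CNS2c |
| 600 | 5000 | positive | none | none | none |

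If 500/µL were instead the single cut, with the second limb starting there too, every row would keep the subtype it has as written.

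**Reading the table.**

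1. Below 5/µL, and at or above 500/µL, the choice of cut makes no difference in these examples.
2. From above 5 to below 500/µL, the first limb alone makes the participant CNS2. The second limb and its algorithm check add nothing for cytospin-positive participants.
3. In that range, eligibility depends on the cut only for algorithm-positive participants (rows 3 and 5). Algorithm-negative participants remain CNS2 under either cut, and only the subtype changes (rows 2 and 4).
4. The definition and its subtype disagree on where the algorithm applies. Row 2 meets the second limb of the definition but not CNS2c.

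**Scope.** Part 2 enrols large B-cell or follicular lymphoma only (Protocol Section 5.1, criterion 2), so criterion 10a can affect only ALL participants in Part 1. Ten of 62 is 16%. That is the size of the ALL group, not the number affected.

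**The case against.** The strongest reply is that the text, taken literally, is determinate on entry. The limbs are joined by "or", so failing the second does not undo meeting the first. All three subtypes use one white-cell cut, so nobody falls into two of them. This stands. A reader might infer that the figures cannot all hold, or that one participant receives two classes under the written rule. The documents do not support that. Two answers arise only if a site takes 5/µL as the dividing line in place of the written 0.5 × 10^9/L. What remains is a 100-fold mismatch with no explanation, a 5/µL cut that has no effect where one would expect it to act, and a subtype that does not match its parent definition.

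A reader might also extend the point to the red-cell figures. They are consistent and need no correction.

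A third inference is that the slip undermines ICANS, because CNS leukemia could be mistaken for it. The documents limit that risk. Criterion 10a already requires the absence of suggestive neurologic symptoms, the note to Protocol Table 12 confines ICANS grading to findings with no other cause, and exclusion criterion 13 lets the investigator exclude anyone whose condition would interfere with interpretation. Analysing ICANS with and without a group that may be empty would be out of proportion.

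Finally, Protocol Table 3, footnote g, says that lumbar puncture is not required and is recorded only if done under standard of care. Some ALL participants may therefore have no CSF count to check. This stands too, and it limits the remedy.

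**Conclusion.** Criterion 10a is wrong as written, at low severity. The 100-fold difference is exact and needs no assumption beyond the unit conversion. That the two limbs were meant to meet at one value is an inference from their structure, not something the Protocol states.

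The possible effect on eligibility is confined to cytospin-positive, algorithm-positive ALL participants in Part 1 with CSF white cells above 5 and below 500/µL. Their number is unknown and may be zero. The ALL group of 10 is an upper limit only if the SAP figure was kept to, and the 16% share should not be quoted as the size of the effect.

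No formal test depends on this. Protocol Section 10.3 plans no hypothesis testing for Part 1, and the Part 2 primary test and sample size are unaffected.

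**What to change.** The sponsor should reconcile the CNS2 definition and CNS2a to CNS2c so that they use one white-cell cut in one unit, with the algorithm condition attached at the same count in the definition and in CNS2c. Which value is right is for the sponsor to confirm; the documents do not settle it.

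Then check the enrolled Part 1 ALL participants who have CSF data, list any whose white-cell count lies between the two figures, and state how many have no CSF count on record. If none falls between them, one sentence in the study report closes the point.

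The cost is a wording correction to one criterion and a chart check of about ten participants. Sample size, endpoints and planned analyses stay as they are.
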